8.0 Study Calendar

STUDY PROCEDURES	Baseline Study Visit One	Baseline Study Visit Two	Follow-up					Final Study Visit One	Final Study Visit Two
	-2 wk	Day 0	2 wk	4 wk	6 wk	8 wk	10 wk	11 wk	Week 12
Consent/Accent	X								
CGM monitoring	X							X	
TADA Dietary Assessment	X		X	X	X	X	X	X	
Oral Glucose Tolerance Testing		X							X

Cardiometabolic outcomes		X							X
Sensory Testing		X							X

To allow for deviations in terms of timing and scheduling of study visits, we will consider variations of +/- 7 days from the scheduled visit.

9.0 Reportable Events

We will report adverse event or unanticipated problems involving risk to participants or other to the IU Human Subjects Office promptly and according to the guidance provided by the IU HRPP Reportable Events Policy and Guidance. Adverse events will be reported promptly, within 5 business days of the study team becoming aware of the event, if they are assessed by the PI as (1) unexpected, (2) related or possibly related to study participation, AND (3) suggests that the research places subject(s) or others at greater risk of harm than was previously known. Collection of adverse events (AE) and serious adverse events (SAE) will begin at the start of interventions.

For this study, the following standard AE definitions are used:

Adverse Event: Any unfavorable and unintended sign (including an abnormal laboratory finding), symptom, or disease temporally associated with the use of a medical treatment or procedure, regardless of whether it is considered related to the medical treatment or procedure.

Serious Adverse Event: Any AE that results in any of the following outcomes:

- Death
- Life-threatening
- Event requiring inpatient hospitalization or prolongation of existing hospitalization
- Persistent or significant disability/incapacity

AEs are graded according to the following scale:

Mild: An experience that is transient and requires no special treatment or intervention. The experience does not generally interfere with usual daily activities. This includes transient laboratory test alterations.

Moderate: An experience that is alleviated with simple therapeutic treatments. The experience impacts usual daily activities. Includes laboratory test alterations indicating injury, but without long-term risk.

Severe: An experience that requires therapeutic intervention. The experience interrupts usual daily activities. If hospitalization (or prolongation of hospitalization) is required for treatment it becomes an SAE.

The study uses the following AE attribution scale:

Not related: The AE is clearly not related to the study procedures (i.e., another cause of the event is most plausible and/or a clinically plausible temporal sequence is inconsistent with the onset of the event).

Possibly related: An event that follows a reasonable temporal sequence from initiation of study procedures, but could readily have been produced by a number of other factors.

Related: The AE is clearly related to the study procedures.

AEs are identified during study visits when subjects are interviewed about recent medical history and a physical examination of the subject. After discharge, AEs are assessed at time of study follow-up visits.

SAEs and specific procedure-associated AEs are reported to the IRB within 24 hours. In addition, all AEs are reported according to the IRB using AE reporting guidelines

Management of risks to the subjects

Expected AEs – Related to Consumption of Sparkling Water

Expected AEs associated with drinking sparkling include: abdominal pain (with acute ingestion of large volumes) or increased tooth sensitivity (studies have shown that sparkling waters minimally erode the enamel of teeth (36)). We expect that occurrence of these adverse event to be rare. According to the American Dental Association, sparkling water has a similar effect on teeth as regular non-carbonated water.

AE Management

We expect study participants to consume sparkling water at levels like consumption of carbonated sodas (e.g. more than 2 drinks per day). We will counsel participants to consume the sparkling water at the rate typical for their consumption of sodas, and to not over consume the sparkling water. If participants experience abdominal pain or tooth sensitivity, we will ask them to discontinue their consumption.

Expected AEs – Related to Blood Draws

Expected AEs associated with blood draws are pain, bruising and lightheadedness. Rarely infection and fainting can occur with drawing blood.

AE Management

Research nurses at the Clinical Research Center and similarly trained study personnel who are experienced in phlebotomy will conduct blood draws.

Expected AEs – Related to oral glucose tolerance testing

Expected AEs associated with OGTT the feeling of nausea after drinking the glucose drink. Pain and small risk of skin bruising, bleeding and infections associated with placement of the catheter and blood draws. Rarely infection, lightheadedness and fainting can occur with drawing blood.

AE Management

Research nurses at the Clinical Research Center and similarly trained study personnel who are experienced in phlebotomy will conduct blood draws.

Expected AEs – Related to continuous glucose monitoring

Expected AEs associated with CGM are a small risk of infection, bruising or nausea during placement of the monitor.

AE Management

To minimize risk, the placement of the CGM will be performed with sterile techniques by the study physician or study nurse.

Expected AEs – Related to monitoring of dietary intake

Expected AEs associated with using instruments to collect dietary intake (TADA, 4 day food records) are feelings of discomfort related to privacy and confidentiality. These tests have been used in previous research, and no adverse events were noted (34).

AE Management

The data is subject to the rules under the Health Insurance and Portability and Accountability Act (HIPPA) regulations (see **Confidentiality** below).

Expected AEs – Related to sensory testing

Expected AEs associated with sensory testing should not exceed those of everyday life, especially for those who drink carbonated beverages. The tests will involve consuming a snack and then tasting small volumes (30 mL) of carbonated beverages with various concentrations of sugar within ranges that are commercially available.

AE Management

We will determine food intolerances or allergies to any ingredient in the drinks before administering the drinks.

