5.0 Study Design

The study design is a prospective observational study in adolescents who are at risk for developing T2D, to evaluate the effectiveness of sparkling water to reduce dietary intake of added sugars and thereby improve glycemia. Study data on consumption and the flavor profile of sparkling water will serve as a measure of acceptability. The study intervention will be to provide carbonated flavored sparkling water for 12 weeks to adolescents who have a usual intake of 2 or more servings of SSB per day and are at a high risk for developing type 2 diabetes. Study measures will be obtained before and after the exposure to carbonated flavored sparkling water and each participant will serve as his/her own control. To encourage the participants to substitute the carbonated flavored sparkling water, study personnel will send them weekly iMessages through the TADA app. In addition, we will monitor the participants' diet, using the TADA app, every two weeks, for 4 days. Study measurements will be obtained at baseline, before the intervention, during and at the end of the 12-week intervention.

Flow diagram for randomized, controlled trial

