7.0 Study Procedures

1. **Description of Intervention - Exposure to Sparkling Water:** During baseline study visit 1, participants will be provided with 4 flavors of sparkling water (1 of each flavor) to sample in the 6 days prior to the beginning of the study. Each participant will be asked to choose the his/her most preferred flavor, which will be used during the 12-week intervention. The intervention will be to provide sparkling water to all participants and ask them to substitute the water in place of sugar sweetened beverages for 12 weeks. We will work with the parents/guardians to determine whether delivery or pickup of the beverages from a store is most feasible. To encourage and remind the participants to drink the sparkling water, study personnel will send iMessages through the TADA app, once a week. To assess the consumption of the sparkling drinks, as well as total dietary intake, the participants will create food records, using the TADA app, at baseline, every two weeks and at the end of the study.
2. **Baseline. Initial Visit One - Obtaining Consent and Glycemia and Dietary Measurements:** This meeting will occur at the Clinical Research Center at Indiana University-Purdue University Indianapolis (CRC IUPUI) . The research team will meet with potential subjects to explain the study and to consent/assent the subject. If consent/assent is obtained, the study physician or study nurse will place the continuing glucose monitor. The researcher will give instruction on tracking dietary intake, using the TADA tool. The consent documents may be mailed to the potential participant prior to the training meeting in order to have time to review them. The visit will take one hour of time. During this visit, participants will also be asked about any food allergies and dietary restrictions. This information will be used to select a snack (granola or breakfast bar type item) for participants to consume before the sensory test during baseline visit two and at the final study visit two. Consumption of the snack ensure the participant is not excessively hungry

before making the sensory ratings (hunger makes energy containing foods more palatable, skewing sensory ratings).

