5. Baseline Study Visit Two: About 1 week after the CGM and diet measures are obtained, the subject will attend a clinic visit at the CRC IUPUI which is part of the Indiana Clinical and Translational Science Institute. The visit will take 3 1/2 hours of time.
6. Oral glucose tolerance test. Oral glucose tolerance testing will be performed during week 0 and week 12, at the CRC IUPUI in the morning after participants have undergone an overnight fast for 8 hours. Blood samples will be obtained at -15, 0, 15, 30, 60, 90,120

minutes, relative to ingestion of a glucose drink at a dose of 1.75 g/kg body weight (maximum 75 g glucose). The procedure will be performed by trained nurses at the Indiana Clinical and Translational Science Institute. Glucose readings are performed at each timepoint using point of care instruments.

7. Cardiometabolic outcomes: Blood samples for glucose, insulin, and blood lipid concentrations will be obtained in the morning after participants have undergone an 8 hour fast. Anthropometrical measures of obesity including height and weight, the body mass index, waist circumference, and sagittal abdominal diameter, will be obtained on weeks 0 and 12 [32]. Blood pressure will be measured after 5 minutes of rest, on the right arm in the supine position, using a sphygmomanometer with an appropriate sized cuff [31].
8. Sensory testing to measure perception of sparkling beverages. After the other measurements are complete, but before the sensory tests, participants will be provided a snack (granola or breakfast bar) in order to alleviate hunger. Sensory tests for will be administered at the baseline and at the end of the study. The sparkling beverages, with and without sugar, will be labeled with randomized 3-digit codes, and presented to participants in counterbalanced order. Participants will rate the samples for their sweetness using a “just about right” visual analog scale, with anchors at: -100, “Not sweet enough”; -50, “Slightly not sweet enough”; 0, “Just about right”; +50, “Slightly too sweet”; and +100 “Too sweet.” Samples will also be rated for liking using a hedonic visual analog scale, with anchors at: -100, “Worst ever”; -50, “Dislike”; 0, “Neutral”; +50, “Like”; +100, “Best ever.” Before and between each sample participants will rinse with water, and a 1-minute break will be enforced between each sample.

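### Read literally, AE and SAE collection need not cover the baseline CGM insertion, the first OGTT or other baseline procedures, and other safety passages conflict with that start rule

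*Protocol*

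**What the plan says.** The start rule is in Protocol Section 9.0: "Collection of adverse events (AE) and serious adverse events (SAE) will begin at the start of interventions". Section 9.0 does not define the plural *interventions*, and neither document gives another start date.

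Elsewhere the singular word refers to the drinks. Section 5.0: "The study intervention will be to provide carbonated flavored sparkling water for 12 weeks to adolescents". Section 7.0, item 1: "The intervention will be to provide sparkling water to all participants and ask them to substitute the water in place of sugar sweetened beverages". Section 5.0 also sets the order: "Study measurements will be obtained at baseline, before the intervention, during and at the end of the 12-week intervention".

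The first procedures come early. At Baseline Visit One, "If consent/assent is obtained, the study physician or study nurse will place the continuing glucose monitor". For the glucose test, "Oral glucose tolerance testing will be performed during week 0 and week 12", and the Section 8.0 calendar puts the first one at Day 0, together with the first sensory test. Four sample drinks are handed out at Baseline Visit One, to be tried in the six days before the study begins.

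Section 9.0 also names harms for these procedures, for example: "Expected AEs associated with CGM are a small risk of infection, bruising or nausea during placement of the monitor". It lists nausea, bruising, infection and fainting for the OGTT and blood draws.

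**The concern.** A safety window that opens with the 12-week supply opens after the first round of invasive procedures. Drinking sparkling water is described as carrying little risk, so much of the foreseeable harm in this study comes from the sensor, the catheter, the blood draws and the glucose load. Half of that exposure is at baseline.

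Staff who follow the sentence literally would have no obligation to record a sensor-site reaction, a faint at the first OGTT, or a serious event between consent and Day 0. A participant who left because of a baseline procedure could leave no AE record. Participants may be as young as 10 (eligibility runs to 21), so the record of procedural burden matters even when the events are mild.

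**Working it through.** The plan states no figure on this point, so the check is one of sequence, followed by a count.

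**1. Order of events (Sections 3.1.d, 7.0 and 8.0)**

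| Step | Timing | Relative to the 12-week supply |
|---|---|---|
| Consent, first CGM insertion, sample drinks | Baseline Visit One (-2 wk in the calendar; 6 days before Week 0 in Section 3.1.d) | Before |
| First OGTT (7 timed samples), first sensory test | Baseline Visit Two, Day 0 | Before, by the Section 5.0 ordering |
| Second CGM insertion | 11 wk | After |
| Second OGTT (7 timed samples), second sensory test | Week 12 | After |

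The calendar and Section 3.1.d differ on when the first CGM is placed, but on either timing it precedes the supply.

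**2. Count on the in-person route, with the start rule read as the 12-week supply**

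- Per participant: 1 of 2 CGM insertions, 1 of 2 OGTTs, and 7 of 14 timed samples precede the start.
- 16 enrolled, no dropout: 16 / (16 + 16) = 16/32 = 50% of each procedure.
- 16 enrolled, 13 completing (the number in the Section 12.0 sample size), with dropouts missing only the final visits: 16 / (16 + 13) = 16/29 = 55%.

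**3. What the missing half costs in information**

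If no event is observed in n procedures, the exact one-sided 95% upper bound on the per-procedure rate is 1 − 0.05^(1/n). Procedures are treated as independent, although two in one participant may not be.

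| Scenario | Collection from the supply | Collection from consent |
|---|---|---|
| No dropout | n = 16: 17.1% | n = 32: 8.9% |
| 13 complete | n = 13: 20.6% | n = 29: 9.8% |

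The earlier start roughly halves the harm rate that a clean record can exclude.

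**4. The same count under other readings of the start rule**

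- If *interventions* includes study procedures, the first CGM insertion opens the window and none of the 32 insertions or 32 OGTTs is left out.
- If the window opens when the sample drinks are handed out at Baseline Visit One, all OGTTs are covered. The first CGM insertion is covered or not depending on the order within that visit, which the protocol does not give.

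The number left out thus runs from 0 to 16 of 32 for each procedure, depending on one undefined word.

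**5. The conflicting passages**

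- Section 9.0's attribution scale relates events to study procedures and, for possibly related events, counts time from when those procedures started, not from when the drinks did.
- Section 9.0 requires SAEs and certain procedure-related AEs to go to the IRB within 24 hours. It does not say which procedure-related events are meant, or from when.
- Section 9.0 (visit interviews and examinations) and Section 10.0 (participant notification, laboratory review at every visit) say how events come to light, but not when collection starts.
- The five-business-day route in Section 9.0 applies only to unexpected events. The baseline procedural harms are listed as expected, so this route would not pick them up.

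**The case against.** The strongest reply is that the rule is ambiguous rather than exclusionary. *Interventions* is plural and undefined, while Sections 5.0 and 7.0 speak of a single intervention. Section 9.0 itself defines an AE by reference to a treatment or a procedure. Item 1 of Section 7.0, headed as the description of the intervention, opens with the sample drinks at Baseline Visit One. The 24-hour duty and the monitoring at every visit carry no start date. A faint at the first OGTT would happen in front of research nurses, and point-of-care glucose is read at every time point.

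Most of this stands. A reader might infer that baseline harms are not collected at all, or that half of all procedural harm goes unrecorded. The documents do not support that: the undated duties may bring some baseline events in, the count is of procedures and not of events, and a delayed reaction that surfaces after the supply starts falls inside the window on any reading. A reader might also infer that a planned safety summary would be biased. Neither Section 12.0 nor the SAP plans one.

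What does not stand is the suggestion that these passages settle the question. None sets an earlier start. The expected-AE lists do not imply one either, since the same procedures recur at weeks 11 and 12. The glucose checks protect the participant but are not AE collection.

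**Conclusion.** The point holds as a conflict within the protocol. The only stated start, read in the protocol's own terms, means that events from the first CGM insertion, first OGTT and blood draws, first sensory test and sampled drinks need not be collected, while other text in Sections 9.0 and 10.0 presumes that procedure-related events count. At most, 16 of 32 CGM insertions and 16 of 32 OGTTs lie before the start (16 of 29 each with 13 completers).

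These figures assume the in-person route, 16 enrolled, and baseline procedures done only in those enrolled. The remote sessions in Section 16.0 describe no CGM or OGTT, so there the point reduces to the first sensory test, and the documents do not say which route was used. The protocol regards the procedural risks as minimal. This is therefore a modest but worthwhile correction to safety capture, with no bearing on the efficacy analysis.

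**What to change.** Reconcile the start rule with the procedure-based text in Sections 9.0 and 10.0. Replacement sentence for Section 9.0: *AEs and SAEs are collected from signed consent/assent, before CGM placement at Baseline Visit One, through Final Study Visit Two.* List events before and after the first day of the 12-week supply separately, so that procedural harms are not mixed with those arising during the supply.

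The SAP, dated 06/28/2024, describes its sensory analyses in the past tense, so an amendment may come too late for some or all participants. If visits are complete, state in the report when collection actually began and recover baseline events from the visit records, including for anyone who left before the supply started.

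The cost of the amendment is one sentence and a few more AE entries, with no added visits or procedures. The retrospective route costs a review of the baseline visit records for about 16 participants.

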10.0 Data Safety Monitoring

Adverse events will be monitored by the co-PIs via notification of the principal investigator by the research subject and by regular review of safety and research labs (at each study visit). Each event will be handled individually. Adverse events or unanticipated problems involving risk to the subjects or others will be reported according to IRB standard operating procedures. If the adverse event represents an unanticipated problem and requires changes to the research protocol or informed consent process/document or other corrective actions in order to protect the safety, welfare, or rights of subjects or others, it will be reported to the IRB using the Prompt Reporting Form within five business days of the investigator becoming aware of the event. Unless determined to not represent an unanticipated problem by RCA staff or the IRB Chair or Chair's designee, the report will be reviewed at a convened IRB meeting for possible action. Any serious unanticipated adverse events will be reported within 24 hours of becoming aware of the event. Any new diagnosis found during a study visit, such as type 2 diabetes, hypertension, or high cholesterol, will be reported to the study subject by [name], MD or trained research staff member, and appropriate referral will be made for treatment.

Potential Risks:

The risks of the study protocol as outlined are considered minimal to the participants.

Consumption of sparkling waters: We expect minimal risks regarding consumption of sparkling waters. For adolescents, who are high consumers of sugar sweetened sodas, the risks of consumption of sparkling waters are no more than those for everyday living.

Blood draws: No more than 150 mL total per subject per study or <3 mL/kg body weight, will be collected, which is the amounts allowed by NIH for children. Blood draws will occur after an 8 hour overnight fast and are likely to be via an antecubital vein and will be used to assess glucose, insulin, blood lipid concentrations and biomarkers of added sugar intake (e.g., ¹³C/¹²C ratio). Pain and bruising and much less likely infection could occur with venipuncture. Lightheadedness and rarely, fainting can also occur with drawing blood.

2 hour oral glucose tolerance testing. The risks associated with an OGTT relate to the placement of a catheter, frequent blood draws over a two hour period and drinking concentrated glucose (75g per serving). This test is frequently done in the clinical and research settings, including in the adolescent population by our research group. The risks to subjects are anticipated to be minimal. There is a small risk of skin bruising, bleeding and infections associated with blood draws from a catheter. There is a small risk of feeling nausea after drinking the glucose drink.

Glucose readings are performed at each timepoint using point of care instruments to monitor for the possibility of hyper and hypoglycemia.

Assessment of Cardiovascular Outcomes: Blood pressure and Waist Circumference: Each of these measures are conducted frequently in the clinical setting and are considered to be minimal in risk to participants.

Continuous glucose monitoring: The continuous glucose monitoring system (CGM) is worn to measure how blood sugar levels change over the day in a free-living environment. A video demonstration is provided here: <https://www.freestylelibre.us/?source=provider.myfreestyle.com> The CGM is worn on the back of upper arm. It is a tiny glucose sensor will be adhered to the arm with a needle inserted just under the skin. We will clean the area and insert the instrument by clamping it under the skin. Tape on the instrument will hold it in place when the participant is wearing it. This device measures and records blood glucose values throughout the day. There is a small risk of infection, bruising or nausea associated when using the continuous glucose monitoring system, however, it does not interfere with regular daily activities. To minimize risk, the placement of the CGM is performed with sterile techniques by the study physician or study nurse.

Monitoring of dietary intake: Subjects will use instruments designed to collect dietary intake (TADA, 4 day food records). The risks involved in these tests do not exceed those of normal, everyday life, especially for those who use cell phones and interact frequently with wearable technology. These tests have been used in previous research, and no adverse events were noted [35]. Risks associated with these procedures are related to confidentiality and privacy. Answering questions may cause feelings of anxiety and discomfort. The data is subject to the rules under the Health Insurance and Portability and Accountability Act (HIPPA) regulations (see **Confidentiality** below).

Sensory Testing: The tests will involve consuming a snack and then tasting small volumes (30 ml) of carbonated beverages with various concentrations of sugar within ranges that are commercially available. For this reason, we expect this testing to involve minimal risk to the participants. We will exclude participants from the study who are allergic or intolerant to the items that we are testing.

Participant Safety: Adolescents will always be accompanied by a guardian for all study visit at the Clinical Research Centers. All clinical protocols are conducted in the Clinical Research Centers under the supervision of a study physician or a research nurse. All members of the study team will undergo CITI training for Biomedical Researchers as well as Good Clinical Practice.

Confidentiality: Participants and their guardian will be asked demographic, family history and other questions related to their health. The loss of confidentiality is related to normal risk of providing similar information in a clinic setting.

A. Adequacy of Protection Against Risks

Protection Against Risks:

Experimental procedures and consent forms will be done in accordance with the Institutional Review Boards of Indiana University and Purdue University. The experimental procedure is described on the consent form and is to be signed before the start of any procedure. The signed consent forms will be stored in our permanent record files. Participants are clearly informed that

they may stop at any time and that they may contact a study investigator directly if there are any adverse effects or concerns.

The study physician ([name]) will administer an appropriate physical exam during screening to ensure all volunteers are relatively healthy. If a child has markedly abnormal laboratories or other measures during screening, he/she will be referred to a physician (the child's PCP and/or TH) immediately for evaluation and treatment. Continuation in the study will be at the discretion of their physician and the clinical and safety team.

Inclusion and Exclusion criteria: Our strict inclusion and exclusion criteria for entry will minimize risks.

These criteria will be evaluated during a screening visit and are listed below:

The inclusion criteria: 1) Girls and boys of all race/ethnic groups, aged 10 to 21 years, who are overweight and obese and have a family history of diabetes or have prediabetes; as defined by the American Diabetes Association [37] 2) Have signed informed consent/assent.

The exclusion criteria are: 1) participant is diagnosed with normal glucose tolerance (NGT); 2) participant is diagnosed with T2D; 3) participant is pregnant; 4) use of medications that affect glucose metabolism (such as glucocorticoid-containing medication or atypical antipsychotics). We will not exclude female participants who are currently using, planning to use, or planning to stop using oral contraceptives; 5) syndromic obesity (such as Prader Willi, hypothalamic obesity, or Laurence-Moon-Biedl).

Training of study personnel: A study nurse will be trained to place the continuous glucose monitor. Trained nurses or phlebotomists at the I-CTSI will perform catheter placement and/or blood draws. Clinical procedures within the I-CTSI facilities will be overseen by a study physician. All research personnel will undergo human subjects CITI training.

Additional Protections Against Risk: Participants may refuse to answer questions on questionnaires or on phone calls with the study personnel. During the OGTT, glucose readings will be performed at each timepoint using point of care instruments to monitor for the possibility of hyper and hypoglycemia. Participants will be asked about any food intolerances or allergies to ingredients before snacks are provided prior to the sensory tests. A snack that offers no risk to participants will be chosen. Adolescents will always be accompanied by a guardian for all study visit at the Clinical Research Center. Regarding using the TADA app on an iPhone, subjects will not incur any costs associated with the use of the iPhone. The iPhones will be provided in protective cases so that it is unlikely that they will be damaged if dropped during everyday use.

